7.11.2 Laboratory Data

The clinical laboratory data will be summarized by scheduled time point, Group, and change from baseline. A listing will be provided where the values that are below the lower limit or above the upper limit of the reference range will be flagged. Those values or changes in values that are considered clinically significant by the investigator will also be flagged in the listing.

Repeated or unscheduled results will not be included in the by timepoint summaries but will be included when looking for extreme values and displayed in the individual data listings.

7.11.3 Vital Signs

Vital signs data will be summarized by time point, Group, and change from baseline. A listing will also be provided.

Repeated or unscheduled results will not be included in the summary statistics but will be included in the individual data listings.

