	
Peritoneal Cytoreductive Surgery ; Groups 1 and 2)
 
Procedures at the time of cytoreductive surgery
 
The following procedures will be performed on the day of surgery:
 
• Record the patient's vital signs (only if they were abnormal on Day 0)• Obtain a blood sample for routine laboratory tests• Record all medications being taken, including prescription, over-the-counter, and herbal medications• Discuss with the patient any new or unexpected changes in they are feeling 
Once the patient is under anesthesia, some procedures will occur that would not normally be part of surgery if the patient were not in this study. The SOC surgical procedures will be allowed to continue with the addition of the imaging steps listed below.
 
• During SOC resection, up to 15 specimens (10 suspected tumor and 5 normal) specimens will be imaged using the intraoperative camera on a section of normal tissue• Once the SOC resection is complete, the surgeon will examine the peritoneal cavity with the intraoperative NIR camera in search of additional fluorescent metastatic disease that was missed during SOC using an assessment method similar to that used for establishing the PCI score (i.e., 13 regions)• Additional fluorescent lesions will be removed and imaged on a section of normal tissue in a manner analogous to the SOC specimens 
Day 10 (± 5 days) or Day of Discharge (Whichever event occurs first)
 
• Record the patient's vital signs• Perform 12-lead ECG to monitor heart activity• Perform a physical examination• Obtain blood samples for routine laboratory tests• Record all medications being taken, including prescription, over-the-counter, and herbal medications• Discuss any new or unexpected changes or adverse events 
Day 28 (± 5 days) after dosing
 
• Obtain blood samples for routine laboratory tests, including a pregnancy test for females who are capable of becoming pregnant• Record all medications they are taking, including prescription, over-the-counter, and herbal medications• Discuss new or unexpected changes in they are feeling• Record vital signs (temperature, heart rate, blood pressure, and breathing rate)

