6.2 Pegsitacianine Administration (Days 0)

Predose procedures

- Confirm eligibility for the study and that medical information is complete
- Record weight and height and calculate BMI
- Discuss how the patient is feeling and their everyday activities
- Record vital signs
- Perform a 12-lead electrocardiogram (ECG) to check the heart activity during pre-operative screening
- Install an IV line
- Obtain blood for routine laboratory tests, including a pregnancy test for females who are capable of becoming pregnant
- Obtain blood, urine, or a breath test to test for alcohol. This test may be performed if relevant to the patient's medical history. If a urine or breath test is used and is positive, a blood test may be used to confirm the test results
- Record all medications taken since the Screening visit, including prescription, over-the-counter, and herbal medications

The Sponsor recommends the use of prophylactic diphenhydramine prior to study drug administration to decrease the possibility of an infusion-related reaction.

Dosing and postdose procedures

Procedures during and after dosing of pegsitacianine are summarized below:

- Dosing of pegsitacianine will be administered through an IV injection
Total dosing time will depend on the patient's body weight and total volume to be administered
- The following postdose assessments and procedures will occur after infusion of the study drug has been completed:
 - Record the patient's vital signs immediately after the infusion and 60 minutes afterward
 - Discuss any new or unexpected changes in how the patient is feeling
 - Record all medications they are taking, including prescription, over-the-counter, and herbal medications

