6.3 Surgery and Follow-up Visits (Group 1 and 2)

Procedures at the time of cytoreductive surgery

The following procedures will be performed on the day of surgery:

- Record the patient's vital signs (only if they were abnormal at dosing)

- Obtain blood for routine laboratory tests
- Record all medications being taken, including prescription, over-the-counter, and herbal medications
- Discuss with the patient any new or unexpected changes they are feeling
- Record any AEs

Once the patient is under anesthesia, some procedures will occur that would not normally be part of surgery if the patient were not in this study. The SOC surgical procedures will be allowed to continue with the addition of the steps listed below.

- During SOC resection, the surgeon will select up to 15 (10 suspected tumor and 5 normal) specimens that will be imaged using the intraoperative camera on a section of normal tissue following excision (*Note: NIR camera should not be used to examine the peritoneal cavity at this time*)
 - A total of up to 15 specimens are to be imaged: 5 representative normal pieces of tissue and 10 individual suspected tumor specimens
 - The SOC specimens are to be resected upon the initiation of surgery and imaged on a section of normal tissue (i.e., mesentery) immediately following the collection of all SOC samples
 - The width of the camera's field of view is to be confined to a distance of 10 cm. A surgical ruler is to be placed in frame to control the width of the field of view
 - Note: while there are no specimen size stipulations provided in this protocol, the samples must be able to be imaged within the 10 cm wide imaging window.
 - For samples with multiple nodules, individual nodules should be dissected away from the bulk sample and imaged individually as single specimens.
 - Representative normal sections of tissue should be imaged in an analogous manner
- Samples will be imaged using the NIR camera and fluorescence status and specimen name will be dictated by the surgeon for documentation by the clinical research coordinator in the provided Imaging Workbook
- Once the SOC resection is complete, the surgeon will dictate their completeness of cytoreduction score to the clinical research coordinator for documentation prior to examining the peritoneal cavity with the intraoperative NIR camera in search of additional fluorescent metastatic disease that was missed during SOC

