7.4 Vital Sign Measurements

Vital sign measurements (systolic and diastolic blood pressure, pulse, respiratory rate, and oral temperature) will be obtained at Screening, Day 0 (Pre/Post dose), Day of Surgery (only if abnormal at dosing), Day 10 (± 5 days) or Day of Discharge and Day 28.

Oral temperature will be documented in degrees Celsius.

Blood pressure and pulse will be measured after a resting period of at least 5 minutes in the supine position with a standard mercury sphygmomanometer or an automated oscillometric blood pressure monitor.

7.5 12-lead Electrocardiogram

A standard safety 12-lead ECG will be conducted on Day 0 (Pre-Dose) and on Day 10 (± 5 days) or Day of Discharge. Additional ECGs may be performed at the discretion of the investigator. The investigator or designee will be responsible for reviewing the ECG to assess whether the ECG is within the reference limits and to determine the clinical significance of the results. These assessments will be recorded in the eCRF.

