13. APPENDIX 1: SCHEDULE OF EVENTS (GROUPS 1 AND 2)

[figure not shown]
Evaluation	Screening	Treatment			
	Days -30 to 0	Day 0	Sur er postdose)	Day 10 (±5 days) or Day of Discharge	Day 28 (± 5 days)
Informed consent & subject enrollment	X				
Inclusion/exclusion criteria	X	X			
Blood/Urine/Breath alcohol		X			
Pregnancy test ^a	X	X			X
Demographic data	X				
Medical history	X				
Physical examination	X			X	
Karnofsky Performance Status	X				
Height ^b	X	X			
Body weight ^b	X	X			
Vital signs ^c	X	X	X ^d	X	X
12-lead electrocardiogram		X ^e		X	
Concomitant medications	X	X	X	X	X
Study drug administration		X ^f			
Adverse events review ^g		X	X	X	X
Serum chemistry	X	X	X	X	X
Hematology ^h	X	X	X	X	X
Surgery			X		
Intraoperative Imaging			X		
Pathology evaluation of surgical specimens			X ⁱ		

Footnotes

[figure not shown]
- ^a For female subjects, a serum sample for a serum pregnancy test will be collected at screening and on Day 0 and Day 28.
- ^b Body mass index will be calculated at Screening only.
- ^c Vital sign measurements will include systolic and diastolic blood pressure, pulse, respiratory rate, and temperature (in degrees Celsius). Blood pressure and pulse will be measured after a resting period of at least 5 minutes in the supine position.
- ^d Vitals are only to be collected if they are found to be abnormal at dosing
- ^e 12-lead ECG is to be performed prior to study drug administration
- ^f Prophylactic diphenhydramine may be administered prior to the administration of pegsitacianine
- ^g Patients will be assessed for AEs occurring from the time of dosing through Day 28 (± 5 days)
- ^h Hematology assessments will include hemoglobin, hematocrit, erythrocyte count (red blood cells), differential leukocytes, platelet count, and total leukocytes (white blood cells).
- ⁱ Pathologic analysis of surgical specimens will take place from the conclusion of surgery and up to 10 days after

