7.3 Definition of Baseline

Baseline is defined as the measurement closest to, but prior to, the administration of study drug. No reassignment of visits will be conducted.

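### Surgery-day vital signs are collected only in patients abnormal at dosing, yet SAP 7.11.3 averages them as change from baseline: the row describes a selected subset and may show a spurious change

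*SAP*

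**What the plan says.** **Collection.** Protocol 6.3, Protocol 7.4, Protocol Appendix 1 (footnote d) and SAP Appendix 1 (footnote d) give one rule for the day of surgery: "Vitals are only to be collected if they are found to be abnormal at dosing". The Protocol Summary words it differently: "Record the patient's vital signs (only if they were abnormal on Day 0". Day 0 itself has a pre-dose reading and, under Protocol 6.2, two more: "Record the patient's vital signs immediately after the infusion and 60 minutes afterward". Neither document defines abnormal or says which of these readings triggers the surgery-day measurement.

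**Baseline.** SAP 7.3: "Baseline is defined as the measurement closest to, but prior to, the administration of study drug". With vital signs scheduled before dosing on Day 0, that is normally the Day 0 pre-dose reading.

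**Analysis.** SAP 7.11.3: "Vital signs data will be summarized by time point, Group, and change from baseline". SAP 7.4 uses observed cases without imputation. SAP 7.11.3 keeps repeated or unscheduled results out of the summary statistics but does not mention the surgery-day reading. Both schedules of events show surgery as a vital-signs column. By contrast, SAP 7.11.4 and 7.11.5 report physical examination and ECG as listings only.

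**The concern.** The collection rule and the summary rule do not fit together. On observed cases, the surgery-day row can contain only patients selected because a dosing-day vital sign was abnormal. The Day 10 (or discharge) and Day 28 rows are scheduled for everyone. A reader who follows the table down its time points would be comparing different sets of patients without being told so.

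The change column has a further problem. If the reading that selects a patient is also the baseline, or is one of several readings that can select, then part of its extremeness is chance. The next measurement is then expected to lie nearer the mean even if the drug does nothing. The trial has a single arm, so no control column would reveal this. Patients selected for high and for low values would also be averaged together, so the pooled change may describe neither.

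Vital-sign abnormalities are part of the secondary safety endpoint in SAP Table 1. What is at stake is the interpretation of one row of a descriptive table.

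**Working it through.** The documents give no figure to reproduce, so the check asks how large the artefact could be and what it depends on.

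**Assumed inputs (none are in the documents).** Systolic pressure with mean 130 and SD 15 mmHg; abnormal means above 140; correlation rho of 0.5 to 0.8 between any two readings; normal distribution; no drug effect. From the documents: about 60 patients, one pre-dose and two post-dose readings on Day 0, and a pre-dose baseline.

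**Step 1: trigger on the pre-dose reading, high values only.** With a = (140 - 130)/15 = 0.667, the share selected is 1 - Phi(a) = 0.252, about 15 of 60. The selected patients' baseline lies 15 x phi(a)/(1 - Phi(a)) = 18.98 above the mean, at 149.0. The expected change is -(1 - rho) x 18.98:
- rho 0.5: -9.5 mmHg
- rho 0.6: -7.6 mmHg
- rho 0.7: -5.7 mmHg
- rho 0.8: -3.8 mmHg

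In simulated trials of 60 patients at rho 0.6, the mean change was -7.6 mmHg. It lay between -14.0 and -1.2 in 95% of trials and was a fall in 99%.

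**Step 2: other readings of the trigger.** These come from a simulation of 1,000,000 patients.

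| Assumed trigger | Share selected | Change, rho 0.5 to 0.8 (mmHg) |
|---|---|---|
| Pre-dose above 140 | 25% | -9.5 to -3.8 |
| Pre-dose above 140 or below 90 | 26% | -9.0 to -3.6 |
| Any of the three Day 0 readings above 140 | 47% to 38% | -2.4 to -1.0 |
| A different vital sign, correlated 0.3 with this one, more than 1 SD high | 16% | -3.4 to -1.4 |
| Post-dose readings only, above 140 | 38% to 33% | about 0 |
| Pre-dose above 150 or below 110 (symmetric) | 18% | about 0 |
| All patients measured | 100% | 0 |

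The symmetric case is near zero only because falls in the high group cancel rises in the low group. The post-dose-only case is near zero because all pairs of readings were given the same correlation. If same-day readings are more alike than readings on different days, some regression returns. For a single post-dose trigger above 140, with correlation 0.8 within the day and 0.6 between days, it is -(0.8 - 0.6) x 18.98 = -3.8 mmHg.

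**Step 3: comparability.** Under the Step 1 trigger at rho 0.6, the surgery-day mean is 130 + 0.6 x 18.98 = 141.4, which is 11.4 above the all-patient mean. The change column in the same row reads -7.6. One column suggests a rise and the other a fall, and neither reflects a drug effect. The row still describes a selected subset when the expected change is zero.

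**The case against.** The strongest reply is that regression to the mean in change from baseline needs selection on the baseline reading or on something more closely tied to it than the surgery-day reading is. The protocol does not say that selection is on the pre-dose value. Infusion reactions are described in Protocol 4.3 as generally starting within 5 minutes of infusion start, so a post-infusion trigger is a plausible reading. Under equal correlations it gives about zero. This stands: neither the size nor the direction of any artefact can be taken from the documents.

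A reader might infer that the table will certainly show a false fall of several mmHg. The documents do not support that. It requires a one-sided trigger on the pre-dose value and numerical inputs that are all assumed. A reader might also infer that surgery day supplies the first post-dose vital signs. It does not, because every patient has readings scheduled immediately and 60 minutes after infusion.

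Two further defences stand only in part. First, SAP 7.2 reports missing and non-missing counts, so the small number would be visible. But values not collected by design would appear as missing, and the table itself would not say how the subset arose. Second, SAP 7.11.3 excludes repeated or unscheduled results, and a reading prompted by an earlier abnormal one might be called a repeat. But the schedule lists it as a conditional visit, so the exclusion does not clearly remove it.

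**Conclusion.** The concern holds in a limited form. Followed as written, the SAP yields a surgery-day row for a subset selected on abnormal dosing-day vital signs. That row is not comparable with the Day 10 and Day 28 rows, whichever Day 0 reading is the trigger. Its change column may show a spurious shift when the pre-dose reading contributes to the trigger.

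Under the assumed systolic values, the shift ranges from about 0, through -2.4 to -1.0 mmHg (any Day 0 reading triggers), to -9.5 to -3.8 mmHg (one-sided pre-dose trigger). These figures illustrate the mechanism; they do not predict this trial's result. Severity is minor: the summary is descriptive, untested and not part of the primary endpoint, and unselected post-infusion readings are available.

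**What to change.** In SAP 7.11.3, exclude the day-of-surgery time point from the pooled mean and change-from-baseline summaries. List those values beside each patient's baseline and the Day 0 values that triggered collection. State the number measured, and label the listing as a subset selected for abnormal dosing-day vital signs. This follows the listing-only handling already used in SAP 7.11.4 and 7.11.5.

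Reconcile the Protocol Summary wording (Day 0) with Protocol 6.3, Protocol 7.4 and both schedules (at dosing), so that the triggering reading is identifiable in the data.

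The cost is a sentence or two in the SAP and one wording reconciliation, with no new data. The loss is one summary row in a descriptive safety table; the individual values remain in the listing.

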7.11.4 Physical Exam

Physical examination results will be provided as a listing.

7.11.5 ECG

ECG results will be provided as a listing.

8. DEVIATIONS FROM ANALYSIS AS DESCRIBED IN THE PROTOCOL

No deviations from the protocol are planned.

9. APPENDIX 1: SCHEDULE OF EVENTS (GROUPS 1 AND 2)

Evaluation	Screening	Treatment			
	Days -30 to -1	Day 0	Surgery	Day 10	Day 28
Informed consent & subject enrollment	X				
Inclusion/exclusion criteria	X	X			
Blood/Urine/Breath alcohol		X			
Pregnancy test (a)	X	X			X
Demographic data	X				
Medical history	X				
Physical examination	X			X	
Karnofsky Performance Status	X				
Height (b)	X	X			
Body weight (b)	X	X			
Vital signs (c)	X	X	X (d)	X	X
12-lead electrocardiogram		X (e)		X	
Concomitant medications	X	X	X	X	X
Study drug administration		X			
Adverse events review (f)		X	X	X	X
Serum chemistry	X	X	X	X	X
Hematology (g)	X	X	X	X	X
Surgery			X		
Intraoperative Imaging			X		
Pathology evaluation of surgical specimens			X (h)		

Footnotes

[REDACTED]

Confidential and Proprietary

Statistical Analysis Plan v3

Effective Date

24 JAN 2023

- ^a For female subjects, a serum sample for a serum pregnancy test will be collected at screening and on Day 0 and Day 28.
- ^b Body mass index will be calculated at Screening only.
- ^c Vital sign measurements will include systolic and diastolic blood pressure, pulse, respiratory rate, and oral temperature (in degrees Celsius). Blood pressure and pulse will be measured after a resting period of at least 5 minutes in the supine position.
- ^d Vitals are only to be collected if they are found to be abnormal at dosing
- ^e 12-lead ECG is to be performed prior to study drug administration
- ^f Patients will be assessed for AEs occurring from the time of dosing through Day 28 (± 5 days)
- ^g Hematology assessments will include hemoglobin, hematocrit, erythrocyte count (red blood cells), differential leukocytes, platelet count, and total leukocytes (white blood cells).
- ^h Pathologic analysis of surgical specimens will take place from the conclusion of surgery and up to 10 days after
